9.2.3. Calculation of the Concordance between dengue RT-qPCR and NS1-antigen

Statistical analysis of concordance will be performed to compare a dengue case detected by RT-qPCR and NS1-antigen

Three 2x2 contingency table will be provided and the following measures of agreement will be calculated as shown in Table 3.

Table 3 Comparison of two diagnostic methods for Dengue cases

Dengue cases		RT-qPCR	
		Positive	Negative
NS1-antigen	Positive	True positive (TP)	False positive (FP)
	Negative	False negative (FN)	True Negative (TN)

- Sensitivity: $TP/ (TP+FN)$
- Specificity: $TN/ (TN+FP)$
- Positive predictive value (PPV): $TP/ (TP+FP)$
- Negative predictive value (NPV): $TN/ (TN+FN)$
- Proportion of overall agreement, which is the proportion of cases similarly classified: $(TP + TN)/ (TP+FP+FN+TN)$.
- Cohen's kappa coefficient. The magnitude of the kappa coefficient represents the proportion of agreement greater than that expected by chance.

9.2.4. Logistic Regression

Univariate and multivariable logistics regression models will be presented. Variables with univariate p-value less than 0.1 will be included in the multivariable model. A step-wise selection using 0.1 as criteria of entering and removing will be used for selection variables in the multivariate analysis.

10. ANNEXES

10.1. Business rules for standard data derivations and statistical methods

This section contains GSK Vaccines' standard rules for data display and derivation for clinical and epidemiological studies. These rules will be applied along with those detailed in section XX (additional study-specific rules).

10.1.1. Handling of missing data

10.1.1.1. Dates

When partially completed dates (i.e. with missing day or month) are used in calculations, the following standard rules will be applied:

- A missing day will be replaced by 15
- A missing day and month will be replaced by June 30th.

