4. CASE DEFINITION

4.1. Acute febrile illness due to LCD

ALL of the following findings must be met for an AFI due to LCD (see [Figure 2](#)):

- Fever (body temperature $\geq 38^{\circ}\text{C}/\geq 100.4^{\circ}\text{F}$) on ≥ 2 consecutive calendar days, measured at least twice, at least 8 hours apart, and
- Laboratory confirmation of dengue through dengue RT-qPCR on the acute serum sample taken during the 7-day period (Days 2-7) from the onset of fever (body temperature $\geq 38^{\circ}\text{C}/\geq 100.4^{\circ}\text{F}$)

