- 5) The subject/subject's parent(s)/LAR(s) will bring the diary card with him/her to each Suspected Dengue Visit. The investigator or appointed study personnel will record the diary card information in the eCRF if a temperature of $\geq 38^{\circ}\text{C}$ ($\geq 100.4^{\circ}\text{F}$) was recorded on ≥ 2 consecutive calendar days, measured at least twice, at least 8 hours apart. The subject/subject's parent(s)/LAR(s) will return the diary card when completed at the next scheduled visit or contact (i.e., at the next home visit or at a Suspected Dengue Visit).
- 6) A new diary card will be issued by the study staff whenever necessary (i.e., if the subject no longer has one, e.g., the previous one was lost or used).
- 7) Only one study conclusion will be conducted, either at Visit 2, or if a suspected dengue case is ongoing at Visit 2, at the last Suspected Dengue Follow-up Visit for the suspected dengue case.

Table 4 Intervals between study visits/contacts

Interval	Optimal length of interval	Allowed interval *
Scheduled Visits:		
Visit 1 (Month 0) → Visit 2 (Month 24)	24 months	23 months - 25 months
Weekly contacts	7 days	6 – 8 days
Unscheduled Visits:		
Onset of fever (body temperature $\geq 38^{\circ}\text{C}/\geq 100.4^{\circ}\text{F}$) (Day 1) → Suspected Dengue First Visit	1 day (on Day 2)	up to 6 days (Day 2 to Day 7) **
Suspected Dengue First Visit → (optional) Return Visit (as per investigator judgement)	1 – 6 days	1 – 6 days
Suspected Dengue First Visit → Suspected Dengue Follow-up Visit	7 – 8 days (may occur during a weekly home visit)	7 – 13 days

* Whenever possible the investigator should arrange study visits/contacts within this interval.

** If the subject has not been evaluated within the 7-day period (Days 2-7) from the onset of fever, the Suspected Dengue First Visit is no longer required and the case will be considered as an undetermined case.

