Although subjects will be instructed to contact the study staff in the event of AFI (fever [body temperature $\geq 38^{\circ}\text{C}/\geq 100.4^{\circ}\text{F}$] on ≥ 2 consecutive calendar days, measured at least twice, at least 8 hours apart), there may be cases where the subject is taken directly to a hospital/clinic (study or non-study health care facility). If this occurs, a family member should inform the study staff as early as possible, and the study staff should contact the hospital/clinic where the subject is hospitalised. In addition, weekly contacts will also be used to identify subjects who have been hospitalised with AFI where study staff has not been informed. In such case, clinical data will be retrospectively collected in the eCRF. The study physician will be responsible for collecting the retrospective data and informing the local study coordinator for appropriate follow-up.

All subjects with AFI who fail to attend a Suspected Dengue Visit as they were directly hospitalised will be recorded as LCD, non-LCD, or undetermined cases depending on the availability and result of the dengue RT-qPCR test. Refer to the SPM for more information.

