9. NON-STANDARD DATA DERIVATION RULES AND STATISTICAL METHODS

9.1. Data derivation

9.1.1. Case Definition

The different case definitions for febrile illness are summarized in Table 2

Table 2 Summary of case definitions

Endpoint	Case definition	Case definition for ad-hoc Analysis
AFI with LCD	
[Fever (body temp \geq 38 C /100.4 F) on at least 2 consecutive days are measured at least twice, at least twice 8 hours apart
 
AND
 
Dengue RT-qPCR result on the acute serum sample taken during the 7-day period from onset of fever is positive
	
[Fever (body temp \geq 38 C /100.4 F) on at least 2 consecutive days are measured at least twice, OR
 
Fever (body temp \geq 38 C /100.4 F) on at least 1 day is measured at least twice 8 hours apart
 
AND
 
Clinical suspicion of dengue base on solicited symptoms],
 
AND
 
Dengue RT-qPCR result on the acute serum sample taken during the 7-day period from onset of fever is positive

DENV – 1 LCD	
[Fever (body temp \geq 38 C /100.4 F) on at least 2 consecutive days are measured at least twice, at least twice 8 hours apart
 
AND
 
Dengue 1 specific RT-qPCR result during the 7-day period from fever is positive
	
[Fever (body temp \geq 38 C /100.4 F) on at least 2 consecutive days are measured at least twice, OR
 
Fever (body temp \geq 38 C /100.4 F) on at least 1 day is measured at least twice 8 hours apart
 
AND
 
Clinical suspicion of dengue base on solicited symptoms],
 
AND
 
Dengue 1 specific RT-qPCR result during the 7-day period from fever is positive

Endpoint	Case definition	Case definition for ad-hoc Analysis
DENV – 2 LCD	
[Fever (body temp \geq 38 C /100.4 F) on at least 2 consecutive days are measured at least twice, at least twice 8 hours apart
 
AND
 
Dengue 2 specific RT-qPCR result during the 7-day period from fever is positive
	
[Fever (body temp \geq 38 C /100.4 F) on at least 2 consecutive days are measured at least twice, OR
 
Fever (body temp \geq 38 C /100.4 F) on at least 1 day is measured at least twice 8 hours apart
 
AND
 
Clinical suspicion of dengue base on solicited symptoms], AND
 
Dengue 2 specific RT-qPCR result during the 7-day period from fever is positive

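### The SAP's partial-date rule has no exception for fever onset, so a missing onset day would usually misclassify the PCR sample window; probably rare, but simple to close

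*SAP*

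**What the plan says.** SAP 10.1.1.1 opens with a general scope: "When partially completed dates (i.e. with missing day or month) are used in calculations, the following standard rules will be applied". Two rules follow: "A missing day will be replaced by 15" and "A missing day and month will be replaced by June 30th". The introduction to SAP 10.1 presents these as company-standard rules, to be read with study-specific rules in a section whose number was left as a placeholder (XX). SAP section 9 (case definitions, incidence rate) and Protocol 9.4 (derived data) contain no partial-date rule, so nothing visible overrides the default.

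Fever onset enters three derivations:

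- **Case status.** Protocol 4.1 requires "Laboratory confirmation of dengue through dengue RT-qPCR on the acute serum sample taken during the 7-day period (Days 2-7) from the onset of fever". SAP Table 2 words the window slightly differently: "Dengue RT-qPCR result on the acute serum sample taken during the 7-day period from onset of fever is positive".
- **Person-time.** SAP 9.2.1 ends the at-risk period at the onset of the event of interest.
- **Age at AFI.** SAP 10.1.2.2 subtracts date of birth from onset date.

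Protocol Table 4 counts onset as Day 1 and allows the Suspected Dengue First Visit "up to 6 days (Day 2 to Day 7") after it.

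**The concern.** A mid-month default suits a medical-history date, where an error of two weeks does no harm. It does not suit a date that anchors a six-day window. The 15th bears no relation to when the subject was seen, bled, admitted or last contacted, although all of those dates are recorded and bound the onset closely.

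Read literally, a PCR-positive subject with fever from 1 March and blood drawn on 3 March, but with the onset day missing, is given an onset of 15 March. The sample then precedes the fever and the episode no longer meets the LCD definition. With no in-window result it would presumably become undetermined. PCR-negative episodes would leave the non-LCD rate by the same route. The most plausible setting is a subject taken straight to hospital, for whom Protocol 6.5.5.1.1 says "clinical data will be retrospectively collected in the eCRF".

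**Working it through.** The plan states no figure on this point to reproduce. As a check on date arithmetic, the worked example in SAP 10.1.2.3 (9 January to 11 September 2018) gives 245 days and 245/365.25 = 0.67 person-years, as printed.

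**Inputs**

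- Window: onset is Day 1 and the sample is drawn on Days 2-7, i.e. onset + 1 to onset + 6 days (Protocol 4.1, Table 4).
- Imputation: the 15th of the recorded month, or 30 June of the recorded year (SAP 10.1.1.1).
- Assumption, not in the documents: true onset is equally likely on every calendar day. All days of 2017-2018 were enumerated (730 days, 24 months); for the day-and-month rule, the 365 days of 2018.

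**Day missing, sample truly in window.** Imputed study day = sample date − 15th + 1. This lies between 2 and 7 only if the sample is dated the 16th to 21st of the onset month. For any true lag of 1 to 6 days, exactly 6 onset days per month satisfy that.

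- Retained: 24 × 6 / 730 = 144/730 = 19.7%. Moved out: 80.3%.
- The result is the same for any mix of sampling days from 2 to 7. By month length it is 1 − 6/28 = 78.6% to 1 − 6/31 = 80.6%.
- With lags equally likely, the sample is too early when onset day + lag < 16. That is 15 − 3.5 = 11.5 onset days per month on average: 24 × 11.5 / 730 = 37.8%. The remaining 42.5% are too late.
- If SAP Table 2 is read as Days 1-7, seven dates pass: 24 × 7 / 730 = 23.0% retained and 77.0% moved out.

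**Day and month missing.** Only samples dated 1 to 6 July pass: 6/365 = 1.6% retained, 98.4% moved out (7/365 = 1.9% and 98.1% for Days 1-7).

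**Opposite error.** For a sample truly drawn on Days 8-14 (lag 7 to 13 days), again 6 onset days per month give a sample dated the 16th to 21st, so 19.7% are moved into the window.

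**Person-time.** Enrolment 20 March, true onset 25 March with the day missing: imputed onset 15 March, follow-up 15 − 20 = −5 days.

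**Scale per affected case.** One truly in-window LCD case with a missing onset day costs 0.80 of a case on average. Over the 3300 person-years of Protocol Table 17 that is 0.80/3300 × 100 = 0.024 per 100 person-years. For comparison, the exact interval in that table for 30 cases runs from 0.61 to 1.30.

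**The case against.** The strongest reply is that the situation should hardly arise. LCD needs fever on at least two consecutive calendar days, so fever must be known to the day. The diary card starts on the day of onset (Protocol 6.5.2.5) and a physician reviews it at the First Visit, at most six days later. Staff must know the day of fever before bleeding, because blood is not drawn on Day 1 and no visit is required after Day 7 (Protocol 6.5.5.1.1). Hospital records may also be used to update the data (Protocol 6.5.3.2). This stands: partial onset dates are probably rare.

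It can also be said that the SAP never states that the window check will use imputed dates, and that data cleaning (Protocol 10.1) would catch a sample dated before onset or a negative follow-up time. The first is true; the reading rests on the general scope of the rule. The second helps only partly: a sample pushed past Day 7 is not impossible on its face and looks like ordinary late sampling. Relying on queries also leaves a written rule that gives the wrong answer.

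A reader might infer three stronger things, none of which the documents support:

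- **That a stated share of the primary rate will be lost.** No document gives the frequency of partial onset dates.
- **That severe cases will be lost selectively.** Retrospective collection after direct hospitalisation makes a partial date more plausible there, but nothing says such dates are partial or how severe those cases are.
- **That the error only removes cases.** It also moves late samples in, so presuming every undated sample to be in window would introduce a bias of its own.

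**Conclusion.** The point holds as a fault in a written rule, of low importance. Applied as it stands to an onset with a missing day, the rule misplaces about four in five truly in-window samples, and nearly all of them when the month is missing too. It brings in about one in five samples truly drawn on Days 8-14, and it can produce negative person-time. These shares rest on onset being spread evenly over calendar days and on the rule applying to the window check as its scope implies. They do not depend on which of Days 2-7 the sample was drawn, and change little if the window is Days 1-7.

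They are conditional on a partial onset date. How often that happens is not stated, so the effect on the primary incidence is likely small and cannot be given as a percentage.

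**What to change.** In SAP 10.1.1.1, exempt AFI fever onset from the 15 / 30 June rule and add:

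1. Onset is taken from the diary card or hospital record where available.
2. Otherwise it is imputed within the interval from the last fever-free contact (or enrolment) to the day before the First Visit or admission, and never before enrolment.
3. An imputed onset does not by itself decide whether a sample is in or out of the window. PCR-positive cases with an imputed onset count as LCD in the primary rate and as undetermined in a sensitivity analysis; their number is reported.

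The recorded day of fever at the visit should not be relied on as a source, because it is not among the items listed for the Suspected Dengue visits in Protocol Tables 3 and 5. The placeholder reference in SAP 10.1 should be completed at the same time.

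The cost is a few sentences and a small amount of programming with dates already collected. If no onset date turns out to be partial, the two versions of the primary rate coincide and nothing else changes.

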10.1.1.2. Laboratory data

Missing laboratory results (including immunological data) will not be replaced.

10.1.1.3. Daily recording of solicited symptoms

10.1.1.3.1. Studies with electronic diaries

For studies using electronic diaries for the collection of solicited symptoms, symptoms will be considered present only when a daily recording of grade 1 or more is present.

10.1.2. Data derivation

10.1.2.1. Age at enrolment

Age of enrolment will be calculated as the difference between the date of enrolment and date of birth, in years, and will be expressed in years. It will be calculated as the number of complete calendar years between the date of birth and the date of vaccination. For example:

DOB = 10SEP1983, Date of enrolment = 09SEP2018 -> Age = 34 years

DOB = 10SEP1983, Date of enrolment = 10SEP2018 -> Age = 35 years

10.1.2.2. Age at time of AFI

The subject age at time AFI will be calculated as the differences between the date of the onset of fever and date of birth in years. It will be calculated as the number of complete calendar years between the date of birth and the date of vaccination. For example:

DOB = 10SEP1983, Date of AFI = 09SEP2018 -> Age = 34 years

DOB = 10SEP1983, Date of AFI = 10SEP2018 -> Age = 35 years

Age at time AFI will also be categorize as following subgroups: < 5 years of age, 5 to 11 years of age, \geq 12 to 17 years of age, and \geq 18 years of age.

10.1.2.3. Person Year

The follow up time at risk for estimation of incidence of AFI due to LCD, non-LCD and each serotype of DENV will calculated as the duration between date of enrolment and date of the first occurrence of AFI or the date of last contact whichever comes first. The person year will be calculated by dividing the duration in days between date of enrolment and date of first occurrence of AFI or the date of last contact whichever comes first by 365.25. For example:

Date of enrolment = 09JAN2018, Date of AFI = 11SEP2018 -> 245 Days/365.25 -> 0.67 PY

The total person-year at risk will be the sum of the follow-up times in years for all individuals.

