- Age in the study will be computed as the difference between the date of enrolment (i.e., date of ICF [and IAF if applicable]) and the date of birth. The age will be expressed in years.
- The subject age at time of AFI will be computed as the difference between the date of the onset of fever (body temperature $\geq 38^{\circ}\text{C}/\geq 100.4^{\circ}\text{F}$) completed on diary card and the date of birth.
- The follow-up time for estimation of incidence of AFI due to LCD, will be computed, for each subject, as the difference between the date of first occurrence of AFI due to LCD (by serotype) or the date of last contact if no LCD occurred (i.e., last weekly Suspected Dengue Follow-up or last Visit) and the date of enrolment.
- The follow-up time for estimation of incidence of AFI due to non-LCD, will be computed, for each subject, as the difference between the date of first occurrence of AFI due to non-LCD or the date of last contact if any (i.e., last weekly Suspected Dengue Follow-up or last Visit) and the date of enrolment.
- The follow-up time for estimation of incidence of AFI due to LCD by DENV-1 type, will be computed, for each subject, as the difference between the date of first occurrence of AFI due to DENV-1 LCD or date of last contact if any (i.e., last weekly Suspected Dengue Follow-up or last Visit) and the date of enrolment. The same computations will be done for DENV-2-3 and 4 specific cases.

- The total person-years at risk will be computed as the sum of the follow-up times in year for each individual.
- The number of consecutive calendar days with fever (body temperature $\geq 38^{\circ}\text{C}/\geq 100.4^{\circ}\text{F}$) used for definition of cases will be computed as the number of consecutive calendar days with fever during the 7-day period following the onset of fever.
- The duration of symptoms will be computed as the number of days with grade 1, 2 or 3 symptoms during the 7 days following the onset of fever.
- For the analysis of solicited symptom, missing or non-evaluable measurements will not be replaced. Therefore the analysis of the solicited symptoms will include only episodes of AFI with documented safety data (i.e., diary card completed).

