5.2. Primary objective

5.2.1. Analysis of primary objective planned in the protocol

The incidence rate of first AFI due to LCD will be calculated along with 95% exact confidence interval. This analysis will be based on the total enrolled set. See section 9.2.1 and section 9.2.2 for details of incident rate and confidence interval calculation respectively.

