5.3. Secondary objective

5.3.1. Analysis of secondary objective planned in the protocol

The incidence rate of first AFI due to LCD by serotype (DENV 1 – 4) and incidence rate of AFI due to non-LCD with 95% exact confidence interval will be calculated for overall and age group (could you please put here the age categories?).

Description of signs and symptoms of AFI due to LCD and due to non-LCD will include the percentage of AFI presenting each sign or symptom (any intensity and grade 3) during the 7-day period from the onset of fever (body temperature 38°C/100.4°F). The sign or symptom of suspected dengue infection is summarized in Table 1. Duration of signs and symptoms will also be described for LCD and non-LCD episodes. Analysis will be done overall and then separately by age group.

Table 1 Solicited symptoms of suspected dengue infection

Signs and symptoms
body temperature and route (minimum of two measurements)
headache / irritability
eye pain
myalgia (muscle pain)
arthralgia (joint pain)
abdominal pain
nausea
vomiting
rash
any bleeding (skin, mouth, anus)
loss of appetite
Fatigue/decrease in normal activity
reduced fluid intake

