9.2. Statistical Method

9.2.1. Computation of incidence rate

The incidence rate of first event (IR, number of first episodes per 1000 person-years) will be calculated by dividing the number of subjects reporting at least one episode of event during the follow-up period by the total person-year at risk.

The person-time at risk for an event of interest (e.g. AFI due to LCD) will be calculated as the duration between the date of enrolment and the end of the at-risk period or the earliest of the following:

- Onset date of event of interest (e.g. first episode of AFI due to LCD)
- Date of last contact
- Date of death.

9.2.2. The method for estimating the CIs for incidence rate not accounting for clustered data

To estimate the confidence interval of the incidence rate, the exact Poisson confidence interval will be used [Clopper, 1934].

If n is the number of subjects presenting a given characteristic among these Ny subjects per year, the true incidence rate per 1000 person-years can be estimated by $(n/Ny)*1000$. Its exact $(1-\alpha)\%$ confidence interval is obtained from:

$CINV(\alpha/2, 2*n)/2/Ny*1000$ as the lower boundary

and

$CINV((1-\alpha)/2, 2*(n+1))/2/Ny*1000$ as the upper boundary.

where $CINV$ (*probability, degrees of freedom*) returns the inverse of the chi-squared probability distribution and α is the type I error rate, which will be 0.05 for calculating a 95% CI.

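### SAP 10.1.2.3 ends time at risk at the first AFI of any cause, against the event-specific stop in SAP 9.2.1 and protocol 9.4, and no precedence is stated

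*SAP*

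**What the plan says.** SAP 10.1.2.3 gives a single person-time rule for LCD, non-LCD and each DENV serotype: the "duration between date of enrolment and date of the first occurrence of AFI or the date of last contact whichever comes first". The next sentence repeats the unqualified term, and the worked example uses a date of AFI with no cause attached. Protocol section 3 defines AFI by fever alone, without reference to the RT-qPCR result.

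SAP 9.2.1 stops person-time at the earliest of three dates. The first is "Onset date of event of interest (e.g. first episode of AFI due to LCD"); the others are last contact and death. The rate is obtained by "dividing the number of subjects reporting at least one episode of event during the follow-up period by the total person-year at risk".

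Protocol 9.4 writes separate stops. For LCD it is "the date of first occurrence of AFI due to LCD (by serotype) or the date of last contact if no LCD occurred". For a serotype it is "the date of first occurrence of AFI due to DENV-1 LCD or date of last contact if any", with the same computation for the other three types. Non-LCD has its own stop at the first non-LCD episode.

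On which rule governs:
- SAP 5.2.1, for the primary rate, says "See section 9.2.1 and section 9.2.2 for details of incident rate and confidence interval calculation respectively".
- SAP 5.3.1 states that the "incidence rate of AFI due to non-LCD with 95% exact confidence interval will be calculated for overall and age group", and covers the serotype rates in the same sentence, but gives no such reference.
- SAP 10.1 says of its own rules: "These rules will be applied along with those detailed in section XX (additional study-specific rules"). The section number was never filled in.
- SAP section 8 lists only tertiary objectives that are omitted. It declares no change to person-time.

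**The concern.** A fever that tests negative for dengue does not remove a subject from risk of dengue. A denominator that stops there discards time during which an LCD case could still occur and be counted.

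The stated numerators are not explicitly cut at that point. SAP 9.2.1 counts subjects with the event during follow-up, and protocol 9.6 counts them over the study period. SAP 9.2.1 divides by total person-years at risk, and that total is exactly what 10.1.2.3 goes on to define. A programmer can therefore arrive at the mismatched pairing by following the text.

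The result would be an LCD incidence that is too high. Protocol 3.1 says the study is to provide incidence data for sizing future vaccine efficacy trials, and an overstated incidence would make such a trial too small.

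**Working it through.** **Inputs.** From protocol 9.2: 2000 subjects, 2 years, drop-out of 10% then 20%, about 3300 person-years (PY), and LCD rates of 0.30 to 1.82 per 100 PY in Table 17. The rate L of a first non-LCD AFI is not given in the documents. It is assumed here, with 0.1, 0.2 and 0.3 per PY as the main range.

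**The plan's own example.** 09 Jan 2018 to 11 Sep 2018 is 245 days, and 245/365.25 = 0.67 PY. This reproduces, but it does not settle the question because the AFI has no stated cause.

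**One subject.** Take a non-LCD AFI at 0.67 years and last contact at 2.0 years, with no LCD. The subject adds 0.67 PY to the LCD denominator under 10.1.2.3, and 2.0 PY under 9.2.1 and protocol 9.4.

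**Cohort, two models.** LCD itself is left out as a stop because it is rare.

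- Model A follows everyone for 3300/2000 = 1.65 years: PY(L) = 2000 × (1 − e^(−1.65L))/L, with PY(0) = 3300.
- Model B applies the drop-out as constant hazards within each year, d1 = −ln 0.9 = 0.1054 and d2 = −ln 0.8 = 0.2231. With a = L + d1 and b = L + d2, PY(L) = 2000 × [(1 − e^(−a))/a + e^(−a)(1 − e^(−b))/b], with PY(0) = 3512.

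If the numerator is not cut, the overstatement is PY(0)/PY(L) − 1. If it is cut at the first AFI, the share of LCD cases lost is 1 − PY(L)/PY(0). The fourth column below applies the overstatement to the 40-case row of Table 17 (40/3300 = 12.1 per 1000 PY).

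| Assumed L per 100 PY | Literal PY (A; B) | LCD overstated (A; B) | 12.1 per 1000 PY becomes | Cases lost if numerator is cut (A; B) |
|---|---|---|---|---|
| 10 | 3042; 3200 | 8.5%; 9.7% | 13.1–13.3 | 7.8%; 8.9% |
| 20 | 2811; 2925 | 17.4%; 20.0% | 14.2–14.6 | 14.8%; 16.7% |
| 30 | 2603; 2683 | 26.8%; 30.9% | 15.4–15.9 | 21.1%; 23.6% |

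Of 40 cases, the last column is roughly 3–4, 6–7 and 8–9. Outside this range, L = 2 per 100 PY gives about 2% overstatement and L = 50 gives 47–54%.

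**Sensitivity to the baseline.** Model B's 3512 PY is above the protocol's 3300, but only the ratio matters. A step version with 90% present in year 1 and 72% in year 2 (1800 + 1440 = 3240 PY) gives 9.7%, 20.0% and 30.8%.

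**Other rates.** At Table 17 LCD rates, stopping non-LCD person-time at an LCD episode raises the non-LCD rate by only 0.2–1.7%. Stopping one serotype's person-time at another serotype's case raises that serotype's rate by at most 1.5% (A) or 1.7% (B). The material effect is non-LCD AFI ending time at risk for LCD and for each serotype. Undetermined AFI would add to it, but no rate is given.

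**The case against.** The best defence is that the wording is shorthand. The sentence in 10.1.2.3 opens by listing LCD, non-LCD and serotypes, so the later bare term may mean the AFI of the type being estimated. Section 10.1 is presented as company-standard rules and carries template residue: its age rules refer to a vaccination date in a study that gives no vaccine. Section 9 holds the non-standard methods, 9.2.1 is written for any event of interest, and the primary analysis is sent there. Overstatement also requires the 10.1.2.3 denominator with an uncut numerator, and no sentence prescribes that pairing outright. Finally, all analyses are descriptive, the non-LCD rate is assumed, and the inflated values for the 40-case row (1.31–1.59 per 100 PY) lie within Table 17's exact interval of 0.87–1.65.

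Much of this stands. The shorthand reading is plausible, the 5.2.1 reference favours the event-specific stop for the primary rate, and the size has no anchor in the documents. It does not remove the conflict:

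- 10.1.2.3 names this study's own endpoints, so it is not untouched template text.
- The 5.2.1 reference is not a rule of precedence, and it does not cover the secondary rates.
- Reading the follow-up period in 9.2.1 as also ending at the first AFI would rescue that numerator, but not the one in protocol 9.6.
- A systematic shift in one direction is not excused by being smaller than the sampling error.

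**Conclusion.** The concern holds. As written, SAP 10.1.2.3 conflicts with SAP 9.2.1 and protocol 9.4, no text resolves the conflict, and no change from the protocol is declared. The direction is certain: literal person-time can only be equal or shorter. The size is illustrative. It rests on the literal reading, an uncut numerator, constant independent hazards and an assumed non-LCD AFI rate. Across 10 to 30 per 100 PY the overstatement of LCD incidence runs from 8% to 31%, and it is negligible if non-LCD AFI is rare. If 9.2.1 is followed throughout, neither the bias nor the loss of cases arises. This should be fixed before analysis. It does not call the design or the data collection into question.

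**What to change.** In SAP 10.1.2.3, end follow-up at the first onset of the event being analysed (LCD, non-LCD, or LCD of the given DENV type), or at last contact or death if earlier. Death is listed in 9.2.1 but missing from 10.1.2.3. State that an AFI of another classification does not end time at risk, and apply the same wording to NS1-positive AFI for consistency. Label the AFI in the worked example with its type. Add a reference to 9.2.1 in SAP 5.3.1. Filling the empty section references in SAP 5 and 10.1 is tidying that can be done in the same edit.

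The cost is a one-sentence correction and cross-references. It restores the protocol's own rule and needs no new data.
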